1 PROTOCOL SUMMARY

1.1 SYNOPSIS

[figure not shown]
Title:	Data-Assisted Approach for High Intensity Medical Weight Loss for Diabetes Remission
Grant Number:	IRB00067950 We will study the efficacy of a high intensity medical weight loss intervention paired with a digital platform to create weight loss and induce remission of T2DM compared to a diabetes self-management education intervention. The digital platform provides the capability to tailor the treatment plan, provide automated support, and alert providers when a participant may need more support from the clinical team. If shown to be efficacious, this research could be highly impactful, causing us to rethink our approach to care for those with T2DM and shift the paradigm for millions of individuals in the US. Furthermore, this approach will demonstrate the feasibility of helping people engage in metabolic treatment strategies in a way that is scalable leveraging digital and mobile solutions that extend the patient-provider relationship, shift care from episodic approaches to more of an on-going model that extends into the life of the patient, while also integrated within the healthcare system workflows.
Objectives*:	
Primary Objective: Test the effectiveness of the combined interventions (data-assisted approach for high intensity medical weight loss) for weight loss in a group of adults with recently diagnosed type 2 diabetes compared to standard of care diabetes self-management education.
 
Secondary Objectives: Demonstrate the feasibility of pairing a high intensity medical weight loss treatment for diabetes remission with a digital platform that integrates remote monitoring, patient self-report, and care pathways into a data-assisted and personalized treatment program.

Endpoints*:	
Primary Endpoint: Change in body weight (kg) from baseline to 12 months
 
Secondary Endpoints: Hemoglobin A1c (%) change from baseline at 3, 6, 9, 12 months Diabetes remission at 12 months, including partial remission (HbA1c of 5.7-6.4% without the use of anti-diabetes

medications) and complete remission (HbA1c of 5.7-6.4% without the use of anti-diabetes medications)

Continuous glucose monitoring outcomes. CGM related outcomes that we will assess at baseline and 12 months include time in range, episodes of hypoglycemia, glucose variability, and average glucose.

Study Population:	Participants will be individuals 18 and older who have T2DM diagnosed within the past 6 years with a BMI of 27-50 kg/m ² . Participants must have an HbA1c between 6.5-11.9%. Sample size will be 30 participants per treatment group.
Phase* or Stage:	Phase 4
Description of Sites/Facilities Enrolling Participants:	Wake Forest Baptist Health Weight Management Center (WMC) Wake Forest Baptist Health Diabetes Center (DC)
Description of Study Intervention/Experimental Manipulation:	Participants randomized to the HIWL treatment group will be placed on a meal replacement-based weight loss protocol. Our active intervention will be delivered with the aid of a technology platform that will automate portions of the intervention and assist clinicians in tailoring treatment and responding to participant needs in a “just-in-time” manner that we frame as a “data-assisted approach.”
Study Duration*:	15 months
Participant Duration:	12 months

1.2 SCHEMA

1.3 SCHEDULE OF ACTIVITIES

Study activity	T<-4	T-4	T-2	0	1	2	3	4	5	6	7	8	9	10	11	12	13	14	15	16	17	18	19	20	21	22	23	24	28	32	36	40	44	48	52	
Phone screen	x																																			
Consent		x																																		
Screen visit (SV) 1		x																																		
History and physical exam		x																																		
Medication review		x																																		
Past medical history		x																																		
Electrocardiogram		x																																		
Center for Epidemiologic Studies Depression Revised Scale		x																																		
SV2			x																																	
EuroQOL-5D			x																									x								x
Diabetes Distress Scale			x																									x								x
Binge Eating Scale			x																									x								x
Yale Food Addiction Scale			x																																	
Dietary intake assessment ¹			x													x												x								x
Physical activity assessment ²			x													x												x								x
Adverse events			x													x												x								x
Randomization				x																																
Treatment orientation				x																																
Lifestyle counseling (Experimental groups)				x	x	x	x	x	After this point, lifestyle counseling will be based on treatment response and guided by data-assisted intervention strategy.																											
Continuous glucose monitoring			x													x												x								x
Body weight		x	x	x												x												x			x					x
Height		x																																		
Blood pressure		x	x	x												x												x			x					x
Pulse		x	x	x												x												x			x					x
Waist circumference		x	x													x												x			x					x
Clinical labs (CMP)					x	x	x	x	x	x						x												x			x					x
HbA1c			x													x												x			x					x
Insulin, lipids, C-peptide			x																									x								x
CBC, CMP			x																																	
Study closeout visit																																				x

1- ASA24 self-administered 24 hour dietary recall

2- Pedometer-<https://www.yamax.co.uk/yamax-pedometers/>

2 Introduction

2.1 STUDY RATIONALE

We will study the efficacy of a high intensity medical weight loss intervention paired with a digital platform to create weight loss and induce remission of T2DM compared to a diabetes self-management education intervention. The digital platform provides the capability to tailor the treatment plan, provide automated support, and alert providers when a participant may need more support from the clinical team. If shown to be efficacious, this research could be highly impactful, causing us to rethink our approach to care for those with T2DM and shift the paradigm for millions of individuals in the US. Furthermore, this approach will demonstrate the feasibility of helping people engage in metabolic treatment strategies in a way that is scalable leveraging digital and mobile solutions that extend the patient-provider relationship, shift care from episodic approaches to more of an on-going model that extends into the life of the patient, while also integrated within the healthcare system workflows.

2.2 BACKGROUND

Largely as a consequence of increasing obesity rates, diabetes prevalence is growing and is predicted to continue to grow in the US. Obesity rates in the U.S. have increased dramatically in the past 3 decades.¹ The increasing rates of obesity have been linked with a higher rate of diseases, including type 2 diabetes mellitus (T2DM).² The association between excessive weight gain and T2DM has been well established, and it is suspected that much of the increased prevalence of T2DM is being driven largely by excessive weight gain.³ It is expected that the prevalence of T2DM could increase from most recent levels in 2015 of 12.2% of US adults aged 18 and older to 25-33% by 2050.⁴

The consequence of a high burden of diabetes is costly for our society. T2DM affects a number of organ systems, which results in significant morbidity and mortality and increased health care costs. The American Diabetes Association estimates that approximately 16% of CVD deaths are attributable to diabetes.^{5,6} It is estimated that approximately 55% of deaths due to renal failure are attributable to diabetes.⁷ As a result of the effect of diabetes on CVD risk, renal function, and other organ systems, diabetes accounted for approximately 246,000 deaths in the U.S.⁷ In 2012, the estimated cost of diabetes was \$245 billion in the US, where an individual with diabetes had an average medical expenditure of \$13,700 annually—2.3 times higher than those without diabetes.⁷

Prevention of T2DM is an important strategy to combat the growing threat that T2DM poses; however, once someone develops T2DM, our options are limited. Our current strategies to deal with diabetes primarily include prevention strategies or, once developed, glycemic and risk factor control. The well-known Diabetes Prevention Program has shown that weight losses of 7% of body weight can lead to over 50% reduction in the incidence of T2DM in people with known impaired fasting glucose or glucose intolerance.⁸⁻¹⁰ While prevention is important, some will develop diabetes despite lifestyle changes, and many others may not have access to or do not avail themselves of preventive treatments. Once a person develops T2DM in our current health care system, the focus is primarily on learning how to live with and manage the disease using education, diabetes medications, and lifestyle changes.^{11,12}

Even when T2DM is well controlled, significant risks and negative impacts associated with living with T2DM still remain. A recent systematic review showed that there was a 30% relative risk increase for severe hypoglycemia when attempting to achieve intensive glycemic control without any significant improvements in risk for all-cause and cardiovascular mortality.¹³ In 5 years, the ACCORD trial reported 19% more deaths in the intensive glucose-management group than in the standard glucose-management group.¹⁴ Recent reports have identified increased risk of all-cause mortality with intensification of T2DM treatment when adding insulin to metformin, raising questions about risks associated with insulin therapy.¹⁵ Additionally, the impact of T2DM on quality of life can be significant. Norris et al pooled data from 118 studies that assessed health related quality of life in persons with T2DM, finding that all 8 component scores of the Short Form-36 were lower than comparable U.S. population norms.¹⁶

We know that diabetes remission can be achieved with significant weight loss in the right patient populations. The landmark DiRECT trial demonstrated that long-term remission of T2DM can be achieved with the use of a total meal replacement diet and achievement of >10% weight loss.¹⁷ After 1 year of treatment, those in the intervention group had a mean weight loss of 10% compared to no weight loss for the control group. The rate of diabetes remission, defined as an hemoglobin A1c of <6.4% was 46% in the treatment group compared to 4% in the control arm. Remission was achieved in 86% of participants who lost at least 15 kg. At 2 years of follow up, the intervention group maintained a lower body weight (-5.4 kg [95% CI, -6.9 to -4]) and HbA1c (-0.44% [-0.76 to -0.13]); the rate of diabetes remission at 2 years was 36% for the intervention group compared to 3% for the control group (aOR 25.82, 8.25 to 80.84; p<0.0001).¹⁸ Participants in this trial were 20-65 years old, had T2DM for <6 years, BMI 27-45 kg/m², and were not on insulin.¹⁷

2.3 RISK/BENEFIT ASSESSMENT

2.3.1 KNOWN POTENTIAL RISKS

There is some minor discomfort and risk of mild bruising during venipuncture.

A breach of participant confidentiality is an additional risk for each participant.

The participants in this study may also be subject to fluctuations in their blood glucose levels as a result of restricting calories and modifying the types of foods they are consuming. This could lead to symptomatic hypoglycemia.

Discomfort associated with venipuncture is rapidly reversible. Bruises from venipuncture will heal in several days. Hypoglycemia is reversible with appropriate therapy.

The continuous glucose monitor will be worn throughout the study for those in the High Intensity Weight Loss Group plus Continuous Glucose Monitoring group and by everyone else during study visits at baseline and weeks 12, 24, and end of study. Use of the continuous glucose monitor could be associated with some skin irritation from the adhesive or the filament that is under the skin. Some people will notice some discomfort with use of the monitor.

2.3.2 KNOWN POTENTIAL BENEFITS

The benefits to participants of participating in the study are that persons may lose weight or changes in body composition may occur. Additionally, many may see improvements in the control of their blood glucose values and lower overall risk of heart disease, heart attacks or stroke. If the study hypotheses are correct, the treatments could make a difference for a lot of people living with diabetes.

2.3.3 ASSESSMENT OF POTENTIAL RISKS AND BENEFITS

The risks to participants in this study are not largely different from what might be experienced in the course of diabetes care and weight loss treatment in the general community, but the potential benefits may be significant especially if persons are able lower their blood glucose levels to the point that they normalize and do not require medication to control their blood glucose.

3 OBJECTIVES AND ENDPOINTS

OBJECTIVES	ENDPOINTS	JUSTIFICATION FOR ENDPOINTS	PUTATIVE MECHANISMS OF ACTION
Primary			
Test the effectiveness of the combined interventions (data-assisted approach for high intensity medical weight loss) for weight loss in a group of adults with recently diagnosed type 2 diabetes compared to standard of care diabetes self-management education.	Change in body weight (kg) from baseline to 12 months	Body weight is primary target for medical weight loss interventions	
Secondary			
Demonstrate the feasibility of pairing a high intensity medical weight loss treatment for diabetes remission with a digital platform that integrates remote monitoring, patient self-report, and care pathways into a data-assisted and personalized treatment program.	Hemoglobin A1c (%) change from baseline at 3, 6, 9, 12 months; Diabetes remission at 12 months, including partial remission (HbA1c of 5.7-6.4% without the use of anti-diabetes medications) and complete remission (HbA1c of 5.7-6.4% without the use of anti-diabetes medications);	As a result of weight change, we expect to see changes in glycemic control.	Reductions in fat mass due to energy restriction, leading to less insulin requirements and greater use of fat stores to make up the energy deficit.
Tertiary/Exploratory			
Demonstrate the impact of including CGM as part of the remote monitoring system with the data-assisted approach for high intensity medical weight loss treatment.	Patient satisfaction with CGM; length of time to achieve A1c goals; study retention	CGM provides immediate feedback to patients about glycemic control. We expect this to improve behavioral reactions and future choices in a shorter term.	Feedback loops with relevant data and clear actions leading to more decisive improvements in biomarkers.
Compare estimated healthcare expenditures and	EuroQOL-5; healthcare utilization from self-report	Intensive weight loss intervention involves cost and time. However,	Weight reduction could decrease healthcare utilization by resolving

OBJECTIVES	ENDPOINTS	JUSTIFICATION FOR ENDPOINTS	PUTATIVE MECHANISMS OF ACTION
utilization between the active treatment groups and the control intervention	and review of medical records	we might expect cost savings due to reduction in weight and improved glycemic control.	obesity related complications and decreasing need for medications and other healthcare.

4 STUDY DESIGN

4.1 OVERALL DESIGN

This project will determine if a data-assisted, high intensity medical weight loss intervention (HIWL) will lead to significant weight loss and diabetes remission in individuals with a BMI 27-50 kg/m² with T2DM of less than 6 years as compared to a diabetes self-management education intervention (DSME). Complete diabetes remission is considered to be achieved when the patient is not taking any anti-diabetes medication for at least 12 months, and the HbA1c is < 5.7%. Partial remission is achieved when the patient is not taking any anti-diabetes medication and has an HbA1c of 5.7-6.4% for at least 12 months. Using a randomized controlled study design, we will randomly assign 90 participants to HIWL, HIWL + CGM, or DSME. Participants assigned to HIWL will receive a high intensity behavioral weight loss intervention delivered using a digital patient engagement platform. Participants will be prescribed a low calorie dietary plan and a recommended physical activity program designed to produce 15-20% weight loss over 12 months. Those assigned to HIWL + CGM will receive the same intervention as HIWL; in addition we will provide them with CGM to use as part of their remote monitoring on a daily basis. Those assigned to DSME will participate in a comprehensive diabetes education program designed to provide education and skills for optimal diabetes management plus lifestyle modification counseling to produce 5% weight loss over the same timeframe. The primary outcome of weight loss will be assessed at 12 months.

4.2 SCIENTIFIC RATIONALE FOR STUDY DESIGN

We will use a randomized controlled trial design to compare the two interventions. This provides the best study design to assign causality and a direct link to our secondary objectives of improved glycemic control.

4.3 JUSTIFICATION FOR INTERVENTION

From a patient-centered perspective, reducing the burden of disease (e.g., medication dosage, diabetes self-monitoring, and diabetes distress) has a direct impact on the individual. From a health system perspective, if those with T2DM cost approximately \$7,700 more annually to care for than those without T2DM⁷, inducing remission saves \$23,100 over 3 years. Based on data from the DiRECT trial, the absolute risk reduction (ARR) at 2 years is 33%; therefore, the number needed to treat (NNT) to achieve one remission is 3 ($1 \div \text{ARR}$). Comparatively, the well-accepted Diabetes Prevention Program had an overall absolute risk reduction of 14.3% compared to placebo, with a NNT of 7.¹⁹ Even if the ARR is adjusted based on modifying the population of patients included in such an intervention (e.g., including people on insulin), an ARR of 20% is still superior to the Diabetes Prevention Program.

To make this type of intervention accessible, we need to demonstrate a model of delivery that is scalable and sustainable. Our application addresses this specific challenge. The Wake Forest Baptist Health Weight Management Center (WMC) has the expertise and infrastructure to deliver total meal replacement diets designed to achieve higher percentages of weight loss. We have demonstrated previously that our mean weight loss achieved in all-comers is higher than that reported in the DiRECT trial. We have also reported improvements in glycemic control and diabetes remission rates. Our intent with this proposal is to pair our proven treatment programs with a digital platform designed to provide a tailored treatment experience that is scalable and sustainable.

Our proposed strategy is to use a combination of software applications, remote monitoring, patient self-reporting tools, and defined care algorithms to create a data-assisted high intensity medical weight loss treatment strategy for diabetes remission. We believe this approach can be effective in engaging patients with the lifestyle and behavior change needed to achieve the treatment goals. By using the digital platform, we can leverage computer automation to expand the reach of individual providers, tailor and personalize treatment immediately based on real-time data flows, and provide assistance in a “just-in-time” fashion that creates efficiency that allows for greater scale of implementation. The shorter latency time between patient need and provider support means that patients will likely stay engaged longer and more consistently to achieve better outcomes. We can also integrate this system with the electronic health record (EHR) providing the patient’s care team a clear view of the actions and resulting impacts of the intervention.

4.4 END-OF-STUDY DEFINITION

This study will be carried out to completion, defined as 12 months of follow up for all enrolled participants.

5 STUDY POPULATION

5.1 INCLUSION CRITERIA

Age 18+	Phone
Type 2 diabetes mellitus by A1c +/- medication ≤ 6 years	Phone
BMI 27-50 kg/m ²	Phone; SV 1
Able to participate in intervention	Phone
Has a mobile phone with text messaging	Phone

5.2 EXCLUSION CRITERIA

Poorly controlled depression (CES-D >16)	Phone; SV 1
Recent hospitalization for psychosis or bipolar disorder	Phone
Poorly controlled blood pressure (>159/99)	SV 1
Prior surgical procedure for weight control	Phone
Unable to make changes to their diet	Phone
Unable to exercise (walk for at least 6 minutes and perform simple strength and stretch exercise tests)	Phone
Use of weight loss medications in previous 3 months	Phone
Recent self-reported weight change (+/- 15lbs)	Phone
Current use of oral corticosteroids more than 5days/month	Phone
Cardiovascular disease event within the past 6 months	Phone
Severe pulmonary disease requiring supplemental oxygen	Phone
Renal failure (end stage renal disease)	Phone
History of non-skin cancer in the past 5 years	Phone
Major liver dysfunction within the last 2 years	Phone
Recently quit smoking less than 6 months prior	Phone
Inability to attend visits and adhere to study protocols	Phone
Pregnancy or currently lactating	Phone

5.3 LIFESTYLE CONSIDERATIONS

During the study, participants will be asked to:

- Refrain from receiving outside treatment for obesity, including other treatment plans, medications, or pursuing surgery
- Avoid pregnancy

Anyone who engages in either will have their study participation closed out.

5.4 SCREEN FAILURES

Screen failures are defined as participants who consent to participate in this study but are not subsequently assigned to the study intervention or entered in the study. Individuals who do not meet the criteria for participation in this trial (screen failure) because of meeting one or more exclusion criteria that are likely to change over time may be rescreened. Examples include the successful treatment of a previous affective disorder, and the lifting of physical activity restrictions previously in place. Rescreened participants will be assigned the same participant number as for the initial screening.

In the case that a participant fails screening due to indications of suicidal ideation (as noted on the CESD-R), the research team will implement an Immediate Action Protocol to address the safety of the participant and ensure appropriate care. The study clinician will be notified and assess the immediate safety of the participant. If the participant is thought to be at high risk for self-harm, an immediate referral to psychiatric care will be initiated. Transportation to the appropriate facility will be arranged. If the participant is not suspected to be high risk and can contract for safety, follow up with psychiatric care will be arranged.

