5.5 STRATEGIES FOR RECRUITMENT AND RETENTION

Potential volunteers for this study will be recruited from the greater Winston-Salem, NC metro area. This is a primary catchment area for Wake Forest Baptist Health, and remains a reliable source of participants for clinical trials conducted by members of this research team. Both Drs. [name] (obesity medicine) and [name] (endocrinology) have clinical programs in the WFBH system that can serve as a source of patients. Patients in these clinics who meet potential eligibility criteria to enroll will be invited to screen for the study. We will also screen medical records using i2b2 and the CTSI to identify potential participants who meet eligibility criteria. Individuals who are identified in the medical record screen will be invited to screen for the study via direct mail. In the direct mail invitation, participants will be able to complete a brief survey to indicate interest in screening for the study. One of the study team members will follow up with the potential volunteer by phone to complete a phone screen. If the potential participant passes the phone screen and is interested in proceeding, he/she will be invited to an in-person screening.

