6.2 FIDELITY

6.2.1 INTERVENTIONIST TRAINING AND TRACKING

Fidelity to treatment impacts reliability and validity of study findings. To ensure consistency of intervention content and delivery, we will use standardized treatment protocols and procedures. A

comprehensive Manual of Operations and Procedures will be developed in the start-up period and distributed to all personnel. Written procedures will exist for assessments, treatment delivery, and monitoring of treatment delivery. Study personnel will be thoroughly trained in the interventions and given corrective feedback in practice sessions. Even among highly trained interventionists, there is a potential for slight deviations from treatment protocol to occur over time, commonly referred to as “intervention drift.” In order to protect against this, regular “booster” training sessions will be conducted. Treatment fidelity will be monitored also by live supervision. The Interventionist will be observed regularly by one of the investigators during group and individual sessions. Live supervision corrects for procedural and intervention drift and enhances adherence to the protocol.

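### Section 5.4 starts the suicidal-ideation safety response only on failing screening for ideation, yet 5.2 lists no such exclusion; the CESD-R response itself should be the trigger

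*Combined protocol and SAP*

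**What the plan says.** Section 5.4 (Screen Failures) gives the condition for the safety response as "In the case that a participant fails screening due to indications of suicidal ideation (as noted on the CESD-R". When it is met, "the research team will implement an Immediate Action Protocol to address the safety of the participant and ensure appropriate care". The steps are concrete. A study clinician is told and judges immediate safety. Someone at high risk is referred at once to psychiatric care, with transport. Someone not at high risk who can contract for safety has psychiatric follow-up arranged.

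The same section begins: "Screen failures are defined as participants who consent to participate in this study" but are then not assigned or entered. It goes on to describe failing screening in terms of meeting exclusion criteria.

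Those criteria are in section 5.2. The depression row reads "Poorly controlled depression (CES-D >16", with the phone screen and SV1 as its check points. The only other mental-health row concerns recent hospitalization for psychosis or bipolar disorder and is checked by phone. Blood pressure, "Poorly controlled blood pressure (>159/99", is checked at SV1. In section 5.1, BMI is checked by phone and at SV1.

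The schedule in section 1.3 marks the "Center for Epidemiologic Studies Depression Revised Scale" once, at T-4, the column that also holds consent and SV1. The phone screen comes earlier.

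**The concern.** Section 5.4 sets two conditions before anyone must act: the person fails screening, and ideation is why. Both concern eligibility. The need for a clinician's assessment comes from what the person disclosed on the scale, and disclosure and eligibility can come apart. If they do, someone who has reported ideation to the study could be randomized, or sent home as a screen failure for another reason, without the written rule requiring that a clinician be told. The CESD-R is not scheduled again after SV1, so the same scale would not give a second chance to notice. What is at stake is participant safety. No estimate, test or interpretation of the trial's outcomes depends on it.

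**Working it through.** No formula applies and the plan gives no figure to reproduce. The check sets the sections side by side.

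**1. Is there an ideation criterion to fail?** Section 5.2 has 17 rows. Two concern mental health (the depression score and recent hospitalization for psychosis or bipolar disorder). None of the 17 names suicidal ideation. The depression row depends on a total score, not on any single response.

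**2. Is there another trigger elsewhere?** Ideation is mentioned only in section 5.4. Sections 8.2 to 8.4 (safety assessments, adverse events, unanticipated problems), the safety oversight section and section 10.1.6 (clinical monitoring) give no trigger for it.

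**3. What can fail a person at the visit where the CESD-R is given?** Listed criteria: 5 inclusion + 17 exclusion = 22. Marked for SV1: depression and blood pressure in 5.2, BMI in 5.1, so 2 + 1 = 3. Not about mood: 3 − 1 = 2 (blood pressure and BMI). Medication review and past medical history are also done at T-4 and could bring other exclusions to light, so 2 is a minimum.

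**4. Apply the 5.4 condition literally to people who endorse ideation at SV1.**

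| Person | Fails a listed criterion? | Fails because of ideation? | Response required as worded? |
|---|---|---|---|
| Total 16 or less, no other exclusion | No | No | No |
| Total 16 or less, fails on blood pressure or BMI | Yes | Not on the listed criteria | Not clearly |
| Total above 16 | Yes | Arguably, through the depression row | Probably |

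The first row is the clearest gap. The second depends on how the reason for failure is recorded.

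**5. How many people?** This cannot be computed. The documents give neither item scoring for the scale nor any rate of ideation by total score. The counts above describe the wording; they do not measure risk.

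**The case against.** The best defence is that 5.4 already makes ideation disqualifying. To speak of failing screening because of ideation on the scale presupposes that ideation is a reason to fail. On that reading the first person in the table does fail, and the response starts. The second person also fails because of ideation, since nothing in 5.4 says it must be the only or the recorded reason. What remains would be a missing row in 5.2. This is a fair reading, and staff who took it would act correctly. It does not settle the matter, because 5.4 itself speaks of meeting exclusion criteria and 5.2 contains none for ideation. A safety step should not rest on staff inferring an unlisted criterion.

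Second, the working detail may be elsewhere. The Immediate Action Protocol is a named procedure that 5.4 only summarises, and section 6.2.1 promises a manual: "Written procedures will exist for assessments, treatment delivery, and monitoring of treatment delivery". That may well supply a sound trigger. It cannot be seen here, and section 6.2.1 does not mention ideation. This limits how far the point can be pressed but does not repair the protocol's wording.

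A reader might also infer a gap at the phone screen: 5.2 lists the depression check there, the call precedes consent, and 5.4 defines screen failures among people who have consented. The documents do not support making this part of the flaw. Section 5.5 says only "One of the study team members will follow up with the potential volunteer by phone to complete a phone screen"; the schedule places the scale at T-4 alone, and nothing puts an ideation question into the call. Adding one would create a pre-consent procedure, and a need for a remote response, that the plan does not now have.

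**Conclusion.** The point stands as a defect in a written safety rule: the trigger is narrower than the response it is meant to start. It should be corrected because the possible harm to one missed person is serious and the correction is small. Its frequency is unknown, and it has no effect on power, analysis or interpretation.

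A reader might infer that participants who report ideation will go without help. The documents do not show that. The response is planned in detail, 5.4 has a reasonable broader reading, and the manual may close the gap.

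The conclusion assumes that the 5.2 cut-off is applied to the scale given at SV1 (5.2 calls it the CES-D; 5.4 and the schedule use the revised version), and that a person can endorse ideation with a total of 16 or less. The documents neither state nor rule out the second assumption.

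**What to change.** Reword the condition in 5.4 along these lines: *Any indication of suicidal ideation on the CESD-R starts the Immediate Action Protocol, whatever the total score or eligibility outcome.*

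Add to 5.2 the ideation exclusion that 5.4 presupposes, checked at SV1, with its clinical threshold set by the investigators. The safety response and the eligibility decision then stand as separate rules, and neither has to be inferred from the other.

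Do not add an ideation check to the phone screen. If someone volunteers ideation during that call, the same clinician notification should apply.

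The cost is one reworded sentence and one added row. The scale is already given at SV1 and the response is already planned. The downside is possibly a few more clinician assessments and screen failures.
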